3.10.2 Epilepsy related variables

The duration of epilepsy is defined as:

$$\begin{aligned} \text{Epilepsy duration (years)} \\ = (\text{Date of informed consent} - \text{date of epilepsy diagnosis})/365.25 \end{aligned}$$

Or if actual dates are unknown, then use relative ages instead:

$$\text{Epilepsy duration (years)} = \text{Age at informed consent} - \text{age at epilepsy diagnosis}.$$

The percent of life with epilepsy is derived as:

$$\text{Percent of life with epilepsy} = \frac{\text{Epilepsy duration}}{\text{Age at informed consent}} * 100$$

3.10.3 Seizures and seizure categories

Each seizure code in the clinical database will be mapped to exclusively 1 of the following seizure types based on the 1981 ILAE classification: IA, IA1, IA2, IA3, IA4, IB, IB1, IB2, IC, IIA, IIB, IIC, IID, IIE, IIF, or III.

With regard to cluster seizures, study sites are to report the number of cluster episodes rather than reporting the estimated number of individual seizures. Therefore, no imputation will be applied for the seizure counts corresponding to reports of cluster seizures. In all the efficacy analyses, clusters will be counted as one seizure (i.e. 1 cluster = 1 seizure) and assigned to the corresponding seizure type.

For the evaluation of this study the categorization of subjects to different seizure categories and the analysis by these seizure categories is essential.

Four different seizure categories need to be distinguished and defined:

- **POS – Partial-onset Seizure**

Subjects are categorized as POS subjects at ScrV if either Partial-Onset Seizure is entered on the “ILAE Seizure Classification History” eCRF page at ScrV or if it has been reported on “Historical Seizure Count” eCRF page for the last 3 weeks prior to ScrV with non-zero value.

- **PGS – Primary Generalized Seizure**

Subjects are categorized as PGS subjects at ScrV if either Typical Absence Seizure, Atypical Absence, Myoclonic, Clonic, Tonic, Tonic-clonic or Atonic Seizure is entered on the “ILAE Seizure Classification History” eCRF page at ScrV or if one of these seizure types has been reported on “Historical Seizure Count” eCRF page for the last 3 weeks prior to ScrV with non-zero value.

- **PGS* – Primary Generalized Seizure excluding Typical Absence**

Subjects are categorized as PGS* subjects at ScrV if either Atypical Absence, Myoclonic, Clonic, Tonic, Tonic-clonic or Atonic Seizure is entered on the “ILAE Seizure Classification History” eCRF page at ScrV or if one of these seizure types has been reported on “Historical Seizure Count” eCRF page for the last 3 weeks prior to ScrV with non-zero value.

- **Typical Absence Seizure**

Subjects are categorized as Typical Absence subjects at ScrV if either Typical Absence Seizure is entered on the “ILAE Seizure Classification History” eCRF page at ScrV or if it has been reported on “Historical Seizure Count” eCRF page for the last 3 weeks prior to ScrV with non-zero value.

If a subject fulfills the requirements for Typical Absence, he is categorized into Typical Absence. Otherwise if the subject fulfills the requirements for PGS*, then he is categorized into PGS*. If the subject only fulfills the requirements for POS, then he is categorized into POS. PGS category is the union of PGS* and Typical Absence categories.

For assignment of EP0065 LTFU subjects to seizure categories the “Historical Seizure Count” eCRF data will be obtained from appropriate EP0065 analysis dataset, whereas “ILAE Seizure Classification History” eCRF data is recorded within N01266.

Subjects which have been rolled-over from core trial N01263 have already been categorized as PGS or POS subjects within core analysis dataset. This categorization will be taken over for N01266 study. The assignment of N01263 subjects to PGS subcategories Typical Absence Seizure or PGS* will be done based on “ILAE Seizure Classification History” eCRF data from N01263 analysis dataset. Subjects who cannot be categorized into any of the above categories will be uncategorized (UNC).

All planned analyses by seizure category (Disposition, Demographic and Baseline Characteristics, safety and efficacy analyses) will use these defined categories. The UNC

category will be presented in Demographic table as a variable and will not be displayed in the tables by seizure category. The UNC will be presented as a seizure category in listings.

3.10.3.1 Derivation of efficacy variables

Efficacy variables will be assessed using the seizure count information recorded on the DRC and EEG data. Seizure count information will be evaluated over the Evaluation Period by 3-month periods based on the DRC (EV until EDV or FV). For DE subjects, seizure count information collected during the Up-Titration Period will be summarized separately. The EEG data will be reviewed at 6 months and yearly thereafter and presented by visit or by study period overall (no time interval presentations planned for EEG).

For subjects coming from core studies EP0065 and N01349 no EEG based values are available which can be obtained as Baseline for N01266. Consequently, these patients will be excluded from any efficacy analysis based on EEG data, where Baseline values are considered. If EEG is done in N01266 at any visit after Baseline, data should be used to assess any variables which do not require Baseline (e.g. seizure freedom).

Similarly, EP0065 and N01349 studies do not provide Baseline DRC data as compared to other core studies. EP0065 and N01349 subjects will be included/excluded in the planned analyses as per following table:

Table 3–6: Inclusion/Exclusion of EP0065 and N01349 data

Analysis	EP0065/N01349 included?
Absolute/percent change in ADF by EEG/	No
Absolute/percent change in 28-days adjusted (POS) seizure frequency by DRC	No
Responder Rate by EEG/ DRC	No
Absolute/percent worsening by EEG/ DRC	No
Seizure free days by DRC	Yes
Seizure freedom by EEG/ DRC	Yes
Average Daily Frequency	Yes (but not to be included in change from Baseline)
New incidence of seizure type	Yes

Calculations based on EEG data (LTFU subjects only)

EEG will be only analyzed for LTFU subjects. The Baseline EEG assessment to confirm POS seizures for DE subjects will not be used to derive efficacy variables. EEG assessments for subjects <2 years of age take 24 hours whereas for subjects ≥ 2 years of age with typical absence seizures only 1-hour EEG assessments were performed.

If the EEG interpretation is different based on EEG data from central reader and from site investigator (response captured in eCRF), then the site investigator interpretation is to be used. Please follow this table:

Table 3–7: EEG interpretation

	Site investigator interpretation = “normal”	Site investigator interpretation = “abnormal”
Central reader interpretation = “Normal”; 0 seizure counts	No problem	Use “Abnormal” with missing counts: ADF missing
Central reader interpretation = “Abnormal”; >0 seizure counts	Use “Normal”; 0 counts	No problem

Calculation of average daily frequency (ADF) of seizures

Average daily frequency (ADF) of seizures based on the EEG data (from central reader or eCRF) is calculated differently for 1-hour and 24-hour EEG:

For 1-hour EEG:

$$\text{ADF} = \text{Number of seizures from EEG data source considered for 1 hour EEG} \times 24$$

For 24-hour EEG (with missing information on interpretable hours):

$$\text{ADF} = \text{Number of seizures from EEG data source considered for 24 hour EEG}$$

For 24-hour EEG (with information on interpretable hours):

$$\text{ADF} = \frac{\text{Number of seizures from EEG data source considered for 24 hour EEG}}{\text{Number of interpretable hours}} \times 24$$

The ADF will be calculated including all seizure types and additionally for POS seizures and PGS seizures, separately.

For certain endpoints, multiple EEG assessments are to be combined. In this instance, for n assessments, average ADF is given as:

$$\text{Average ADF} = \frac{\sum_{i=1}^n \text{ADF}_i}{n}.$$

Calculation of absolute change/worsening in ADF of seizures

Absolute change in ADF is calculated as:

$$\text{Absolute Change in ADF} = \text{Baseline ADF} - \text{postBaseline ADF}.$$

Both absolute changes will be calculated, with ADF including all seizure types and additionally based on POS seizures only.

Absolute worsening in PGS ADF is calculated as:

$$\text{Absolute Worsening in PGS ADF} = \text{postBaseline PGS ADF} - \text{Baseline PGS ADF}.$$

Calculation of percent change/worsening in ADF of seizures

Percent change in ADF is calculated as:

$$\text{Percent Change in ADF} = \frac{\text{Absolute Change in ADF}}{\text{Baseline ADF}} \times 100.$$

Both percent changes will be calculated, with ADF including all seizure types and additionally based on POS seizures only.

Percent worsening in PGS ADF is calculated as:

$$\text{Percent Worsening in PGS ADF} = \frac{\text{Absolute Worsening in PGS ADF}}{\text{Baseline PGS ADF}} \times 100.$$

Calculation of response

Response is defined to be equal to 1 for Percent Change in ADF $\geq 50\%$ and 0 for $< 50\%$. Both responses will be calculated, with percent change in ADF including all seizure types and additionally based on POS seizures only.

For subjects < 2 years of age response is based on the 24-hour EEGs performed over the Evaluation and Down-Titration Period separately.

For subjects ≥ 2 years of age with typical absence seizures categorization, response is based on the 1-hour EEGs performed over the Evaluation and Down-Titration Period separately.

Calculation of Seizure freedom

The categorical variable Seizure freedom is defined to be equal to 1 if none of the EEG assessments within the reported time period (Evaluation Period or Down-Titration Period) have shown occurrence of any seizures and 0 otherwise.

For subjects < 2 years of age seizure freedom is based on the 24-hour EEGs performed over the Evaluation and Down-Titration Period separately.

For subjects ≥ 2 years of age with typical absence seizures categorization, seizure freedom is based on the 1-hour EEGs performed over the Evaluation and Down-Titration Period separately.

Calculation of Seizure freedom rate

Seizure freedom rate will be determined as follows:

$$\text{Seizure freedom rate of Time Period} = 100 \times \left[\frac{\text{Number of subjects who were seizure free over reported Time Period}}{\text{Number of subjects who entered reported Time Period with at least one evaluable EEG assessment during the Time Period}} \right]$$

The denominator includes only those subjects applicable, depending on age group and seizure categorization. See calculation of Seizure freedom.

Calculations based on DRC data

DRC data will be analyzed for DE and LTFU subjects.

Calculation of average daily frequency (ADF) of seizures and 28-day adjusted seizure frequency

Average daily frequency (ADF) of seizures based on the DRC data is calculated over the Evaluation Period, by visit and by 3-month time intervals:

$$ADF = \frac{\sum_{i=1}^n \text{seizure count entered at day } i}{n},$$

where n is the number of days with non-missing seizure count entry in the DRC during the reporting time period. The reporting time period includes the start date but excludes the stop date of the time period.

For DE subjects, Baseline ADF will take DRC data from ScrV to TV1 into account only. For LTFU subjects, Baseline diary data is obtained from Baseline of the core study.

The ADF will be calculated including counts for all seizure types and additionally for POS seizures only.

The 28-day adjusted seizure frequency is calculated as:

$$\text{28day adjusted seizures frequency} = \text{ADF} \times 28$$

The Baseline 28-day adjusted seizure frequency will be calculated using the Baseline ADF.

The 28-day adjusted POS seizure frequency will be calculated using the POS ADF respectively.

Calculation of absolute change/worsening in 28-day adjusted seizure frequency

Absolute change in 28-day adjusted seizure frequency is calculated as:

$$\begin{aligned} \text{Absolute Change in 28 day adjusted seizure frequency} \\ = \text{Baseline 28 day adjusted seizure frequency} \\ - \text{postBaseline 28 day adjusted seizure frequency.} \end{aligned}$$

Absolute change in 28-day adjusted POS frequency is calculated similarly including 28-day adjusted POS frequencies.

Absolute worsening in 28-day adjusted seizure frequency is calculated as:

$$\begin{aligned} \text{Absolute Worsening in 28 day adjusted seizure frequency} \\ = \text{postBaseline 28 day adjusted seizure frequency} \\ - \text{Baseline 28 day adjusted seizure frequency.} \end{aligned}$$

Calculation of percent change/worsening in 28-day adjusted seizure frequency

Percent change in 28-day adjusted seizure frequency is calculated as:

$$\text{Percent Change} = \frac{\text{Absolute Change in 28 day adjusted seizure frequency}}{\text{Baseline 28 day adjusted seizure frequency}} \times 100$$

Percent change in 28-day adjusted POS frequency is calculated similarly including 28-day adjusted POS frequencies.

Percent worsening in 28-day adjusted seizure frequency is calculated as:

$$\text{Percent Worsening} = \frac{\text{Absolute Worsening in 28 day adjusted seizure frequency}}{\text{Baseline 28 day adjusted seizure frequency}} \times 100$$

Calculation of response

Response is defined to be equal to 1 for Percent Change in 28-day adjusted seizure frequency $\geq 50\%$ and 0 for $< 50\%$.

Response will be calculated in both ways: based on 28-day adjusted seizure frequency, including all seizure types, and based on 28-day adjusted POS frequency, including POS seizures only.

The responder rate is based on the DRC data performed over Up-Titration, Evaluation and Down-Titration Period separately.

Calculation of Proportion of seizure free days

The proportion of seizure free days is calculated as:

$$\text{Proportion of Seizure free days} = \frac{\text{Number of Days with no Seizures on DRC Data}}{\text{Number of Days of recorded DRC Data}}$$

All seizure types will be taken into account. The proportion of seizure free days will be calculated over Evaluation Period, by visit and by 3-month time intervals.

Calculation of Seizure freedom

The categorical variable Seizure freedom is defined to be equal to 1 if the following criteria are fulfilled:

Criterion 1: A subject completed the reported Time Period

- Up-Titration Period: for DE subjects only, if at least one eCRF during Up-Titration Period is entered (only Baseline/TV1, Baseline/TV1 and TV2 or Baseline/TV1, TV2 and TV3 could be entered, dependent on subject's individual titration)
- Evaluation Period: if the FV or EDV eCRF page (named FIN) is entered
- Down-Titration Period: if the eCRF DTV page is entered (DTV is the final visit for the Down-Titration Period)

Criterion 2: The seizure diary was completed for at least 90% of days from start date of the appropriate Time Period up to the day prior to the end date of the appropriate Time Period.

Criterion 3: All entered seizure codes have a count of 0 from the day after start date of appropriate Time Period (ie, not including the start date of appropriate Time Period) up to and including the end date of the appropriate Time Period. (If a seizure code is entered, a missing count will lead to a violation of this criteria, too.)

If one of the criteria is not fulfilled, Seizure freedom is defined to be equal to 0.

Seizure freedom will be based on DRC data collected over the Up-Titration, Evaluation and Down-Titration Period separately. All seizure types will be taken into account.

Calculation of Seizure freedom rate

Seizure freedom rate will be determined as follows:

$$\text{Seizure freedom rate of Time Period} = 100 \times \left[\frac{\text{Number of subjects who were seizure free over reported Time Period}}{\text{Number of subjects who entered reported Time Period with at least one DRC entry during the Time Period}} \right]$$

All seizure types will be taken into account.

Calculation of Seizure freedom by visit

The categorical variable Seizure freedom by visit is defined to be equal to 1 if the following criteria are fulfilled:

Criterion 1: The question "Have there been any seizures since the last visit?" has been answered with "No" and all entered seizure codes in the DCR have a count of 0 since prior visit. (If a seizure code is entered, a missing count will lead to a violation of this criteria, too.)

Criterion 2: The seizure diary was completed for at least 90% of days since prior visit. The percentage of days for which diary data were entered since the prior visit will be calculated as follows:

$$\% \text{ of days diary was done} = 100 \times \left[\frac{\text{Days since prior visit} - \text{number of days diary was not done in the interval}}{\text{Days since prior visit}} \right]$$

If one of the criteria is not fulfilled, Seizure freedom by visit is defined to be equal to 0.

Seizure freedom by visit will be based on DRC data and eCRF data collected over the Up-Titration, Evaluation and Down-Titration Period separately. All seizure types will be taken into account.

Calculation of seizure freedom by time interval

The categorical variable Seizure freedom by time interval is defined to be equal to 1 if the following criteria are fulfilled:

Criterion 1: All entered seizure codes have a count of 0 from the day after start date of appropriate time interval (i.e., not including the start date of appropriate time interval) up to and including the end date of the appropriate time interval. (If a seizure code is entered, a missing count will lead to a violation of this criteria, too.)

Criterion 2: The seizure diary was completed for at least 90% within the time interval. The percentage of days for which diary data was completed within a given 6-month interval will be calculated as follows based on a 30-day month:

$$\% \text{ of days diary was done} = 100 \times \left[\frac{180 - \text{number of days diary was not done in the interval}}{180} \right]$$

A similar calculation applies for 3-month seizure freedom based on 90 days and 12-month seizure freedom based on 360 days.

If one of the criteria is not fulfilled, Seizure freedom by time interval is defined to be equal to 0.

Seizure freedom by time interval will be based on DRC data collected over the Up-Titration, Evaluation and Down-Titration Period separately. All seizure types will be taken into account.

Calculation of Incidences for new seizure types

To calculate incidences of new seizure types and subtypes a shift table from Present at Baseline (Yes, No, Missing, Total) to Present during Evaluation Period (Yes, No, Missing, Total) will be prepared. Subjects who do not have results for subtypes at Baseline will be presented with “not assessed” Baseline results and their respective Evaluation Period result. Whenever only subtype information is available the seizure type results will be derived as follows:

- Seizure type I is Present at Baseline = “Yes” if at least one of the subtypes IA, IB, IC is present at Baseline. It is Present at Baseline = “Missing” if data for all subtypes is missing. Otherwise, Present at Baseline = “No”.
(Same rule is to apply to summarize sub-subtypes IA1, IA2, IA3 and IA4 into IA. IA is Present at Baseline = “Yes” if at least one of the subtypes IA1, IA2, IA3 or IA4 is present at

Baseline. IA is Present at Baseline = “Missing” if data for all sub-subtypes is missing. Otherwise, Present at Baseline = “No”.)

- Seizure type II is Present at Baseline = “Yes” if at least one of the subtypes IIA, IIB, IIC, IID, IIE, IIF is present at Baseline. It is Present at Baseline = “Missing” if data for all subtypes is missing. Otherwise, Present at Baseline = “No”.
- Seizure type III does not have subtypes, so derivations are not applicable.

Incidences are the percentages for seizures which were not present at Baseline but present during Evaluation Period:

$$\text{Incidence of seizure type} = \frac{\text{Count of subjects with seizure (sub)type not present at Baseline but present in Evaluation Period}}{\text{Total number of subjects with seizure (sub)type not present at Baseline}}$$

Incidences will be calculated separately for Down-Titration Period.

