3.2.3 Study periods

[Table 3–1](#) shows which study periods are applicable to DE and LTFU subjects:

This document cannot be used to support any marketing authorization application and any extensions or variations thereof.
PUBLIC COPY

Table 3-1: Study periods

Period		Screening Period	Up-Titration Period			Evaluation Period							Down-Titration Period	Safety Period		
Subjects	Visit	ScrV	TV1	TV2	TV2	EV	MEV	FEV	MEV	FEV	MEV	YEV	...	FV/EDV	DTV	SV
			V1	V2	V3	V4	V5	V6	V7	...						
Subjects	DE	x	x	x	x	x	x	x	x	x	x	x	x	x	(x)	(x)
	LTFU					x	x	x	x	x	x	x	x	x	(x)	(x)
	Early Discontinuations												x	x	x	x

(x) – only applicable if the subject does not switch to another BRV study or is taking marketed drug after FV

The study is divided into 5 periods: Screening Period, Up-Titration Period, Evaluation Period, Down-Titration Period, and the Safety Period.

There is a Screening Period for all DE subjects. For DE subjects, this comprises assessments performed prior to the first dose of BRV in N01266. So start date of Screening Period is date of written informed consent and end date is the day before first dose of BRV (TV1-1). Although, patients in LTFU studies will not attend a screening visit, the screening information comprises information collected at various assessments during the core study and consequently will have been collected at different times depending on the domain. Domain specific information is detailed in Section 3.3.

The Up-Titration Period is only applicable to DE subjects, and the start date is the date of the first dose of BRV. The following algorithm is used to determine the end date:

- If the subject enters the Evaluation Period, the date 1 day prior to the EV is the end date
- If the subject does not enter Evaluation Period, the Up-Titration Period ends on the date of the final dose of BRV

For the Evaluation Period, the start date is the date of the first dose of BRV on or after the EV date, and the following algorithm is used to determine the end date:

- If the subject continues the study until it ends, the Evaluation Period ends on the date of FV
- If the subject prematurely discontinues the study, the date of EDV is the end date

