4.2 Handling of dropouts or missing data

The method for handling missing and partial data for medications and AEs is described in Section 3.10.4.1 and Section 3.2.3.1 respectively. Missing AE intensity or relationship will be imputed according to worst case scenario with severe intensity and assumed to be related. For other safety variables, no imputation methods are planned.

Regarding efficacy variables, endpoints using seizure frequency and seizure free days based on DRC data will be calculated over non-missing diary days during each study period or time interval as described in Section 3.10.3.1; days for which seizure diary data were not obtained will not be considered in the calculation of seizure frequency or seizure days. This is applicable to the analysis taking all seizure categories into account as well as to the analysis taking only POS seizures into account. Generally, compliance with the daily seizure diary is expected to be high in a refractory population and, therefore, the impact of missing diary data is expected to be minimal. Because the evaluation of efficacy is not the primary objective of this study, and because this is an uncontrolled study in a variable setting, which allows individualized optimization of dosing of BRV and concomitant AEDs, no summaries assessing the impact of missing seizure diary days are planned.

For subjects who prematurely discontinue during the Up-Titration, Evaluation or Down-Titration Period, the calculation of seizure frequency, seizure free days and seizure freedom will be based on available seizure diary days while the subject was receiving BRV. This effectively imputes the unobserved seizure frequency after discontinuation with the seizure frequency observed prior to discontinuation. The presence of such dropouts may influence the evaluation of the long-term outcomes for subjects who either do not discontinue or do not discontinue early in the study. Therefore, as described below, selected summaries will be produced by exposure duration cohorts to allow an assessment of long-term outcomes without the potentially confounding influence of earlier discontinuations.

Endpoints using seizure data from EEG will only include available data. No imputation method will be conducted.

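### Diary-based seizure freedom over the Evaluation Period can be earned by a short, seizure-free stay before early discontinuation, and the plan tables no fixed-interval or exposure-cohort summary to offset this for most subjects

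*SAP*

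**What the plan says.** SAP Section 3.10.3.1 sets three criteria for seizure freedom from the daily record card (DRC) over a study period.

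- The first is headed "Criterion 1: A subject completed the reported Time Period". For the Evaluation Period it is satisfied thus: "Evaluation Period: if the FV or EDV eCRF page (named FIN) is entered". FV is the Final Visit and EDV the Early Discontinuation Visit.
- The second is diary completeness: "The seizure diary was completed for at least 90% of days from start date of the appropriate Time Period", up to the day before the period ends.
- The third is zero counts: "All entered seizure codes have a count of 0 from the day after start date of appropriate Time Period", through the end date.

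The denominator of the rate is "Number of subjects who entered reported Time Period with at least one DRC entry during the Time Period".

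Section 3.2.3 fixes the end of the Evaluation Period for a child who leaves: "If the subject prematurely discontinues the study, the date of EDV is the end date". No minimum length is set.

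Section 4.2 states that for premature discontinuers "the calculation of seizure frequency, seizure free days and seizure freedom will be based on available seizure diary days while the subject was receiving BRV", and adds: "This effectively imputes the unobserved seizure frequency after discontinuation with the seizure frequency observed prior to discontinuation". It acknowledges that dropouts may influence long-term results and announces selected summaries by exposure duration cohort.

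Section 9.2 presents seizure freedom over the Evaluation Period. It repeats the summary by visit and by 3-month interval only for subjects under 2 years, or 2 years and older with typical absence seizures. It mentions no exposure cohort. Section 3.2.4 says 6- and 12-month intervals will be calculated for seizure freedom, and Section 3.10.3.1 defines a by-interval version on fixed lengths of 90, 180 and 360 days.

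**The concern.** The heading of Criterion 1 promises completion, yet the page of a child who stopped early satisfies it. Because the period shrinks to that child's own follow-up, the other two criteria become easier to meet the sooner the child leaves. A withdrawal after two seizure-free weeks enters the numerator alongside a child free of seizures for years. One seizure in a long follow-up puts a child at 0.

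Compared with scoring withdrawals as not seizure-free, the rule can only push the percentage up. An efficacy figure may thus rise with early discontinuation, whatever the reason for it. For subjects aged 2 years and older without typical absence seizures, this pooled percentage is the only diary-based seizure-freedom summary that Section 9.2 plans, so the reader of the report has no other figure to set against it.

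**Working it through.** The SAP states no seizure-freedom rate, withdrawal share or seizure rate, so there is no figure of its own to reproduce. The check is in three parts.

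**1. Apply the rule as written.** Take a child with an EDV page, all counts 0, and just enough diary days. Counting the period as *d* days, the minimum is 0.9 × *d*, rounded up:

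- *d* = 7: 6.3, so 7 days
- *d* = 14: 12.6, so 13 days
- *d* = 30: 27 days
- *d* = 90: 81 days

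In each case all three criteria are met and seizure freedom = 1. If an EDV page did not count as completion, each would be 0. A child followed for 1,080 days with a single seizure scores 0.

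**2. Compare with the plan's by-interval definition.** There the diary percentage uses a fixed denominator. Treating days after withdrawal as days without diary, the child who leaves with 14 diary days reaches:

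- 14/90 = 15.6%
- 14/180 = 7.8%
- 14/360 = 3.9%

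All are below 90%, so this definition gives no credit. The two definitions disagree on the same child, and Section 9.2 tables the interval version only for the restricted group and only at 3 months.

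**3. Illustrate the size.** Assume seizures follow a Poisson process with a constant rate *r* per 28 days, unrelated to withdrawal. The chance of no seizure by day *d* is

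P0 = exp(−*r* × *d* / 28).

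If a share *w* of subjects leaves near day *d* with adequate diaries, the rate exceeds the one with withdrawals scored 0 by *w* × P0. With *w* = 10%:

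| Seizures per 28 days | P0, Day 14 | Added points | P0, Day 30 | Added points |
|---|---|---|---|---|
| 1 | exp(−0.500) = 0.607 | 6.1 | exp(−1.071) = 0.343 | 3.4 |
| 2 | exp(−1.000) = 0.368 | 3.7 | exp(−2.143) = 0.117 | 1.2 |
| 4 | exp(−2.000) = 0.135 | 1.4 | exp(−4.286) = 0.014 | 0.1 |

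At Day 90 and 1 seizure per 28 days, P0 = exp(−3.214) = 0.040, or 0.4 points. Over 360 days P0 is below 0.001% at all three rates. The added points scale in proportion to *w*. Both *r* and *w* are assumptions.

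**The case against.** **The choice is disclosed.** Section 4.2 names seizure freedom explicitly, says what the available-data approach implies, and announces exposure-cohort summaries. A reader might infer that the plan conceals the treatment of dropouts. It does not. What stands is that Section 9.2 does not carry the announced mitigation through to seizure freedom.

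**The heading may only be loose.** Since a discontinuer's period ends at the EDV, that page documents the end of the period, and Criterion 1 still excludes a child with no final page. This is a fair reading of the bullet. It does not remove the effect, because no minimum duration is set.

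**Very early exits may be uncommon.** Directly enrolled children enter the Evaluation Period only after 7 ± 2 days on a dose with acceptable tolerability and seizure control. The others come from another brivaracetam study. The first scheduled visit after entry falls at 30 ± 7 days. A reader might take the 6.1 points as typical, but that value needs exits near Day 14 and a low seizure rate. The Day 30 column deserves equal weight.

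**Scoring every EDV as 0 is not a clean cure.** Participation ends at varying times for completers too (Section 2.3.3), so mixed follow-up would remain. A child who leaves after years without seizures would also become a failure. This stands, and it is why fixed intervals are the main remedy.

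**Weight.** Seizure freedom is listed among the other variables, all efficacy is exploratory, and nothing is tested. Disposition, Kaplan-Meier retention and exposure tables will show short follow-up at study level. Seizure freedom in Up-Titration has a loose completion rule as well, but Section 9 lists those data only unless otherwise mentioned, so no point is made of it.

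**Conclusion.** The point holds as a defect of definition and reporting. An EDV page with at least 90% diary completion and zero counts yields seizure freedom over the Evaluation Period whatever the length of stay. For subjects aged 2 years and older without typical absence seizures, no planned table corrects for that. The EDV page alone is not enough; the other two criteria must also be met, which is easier over a short stay.

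The direction is upward relative to scoring withdrawals as 0. The amount is unknown. Under the constant-rate assumption with 1 to 4 seizures per 28 days, each 10% of subjects leaving adds about 1.4 to 6.1 points at Day 14 and 0.1 to 3.4 points at Day 30.

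A reader might go further and infer that the study's conclusions are compromised, or that poor tolerability will inflate efficacy by several points. The document supports neither: the primary variables are adverse events, and it gives no withdrawal or seizure rates. It is worth correcting before the tables are produced, because the change is cheap and alters a reported result.

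**What to change.** 1. In Section 9.2, present DRC seizure freedom for all Full Analysis Set subjects by the fixed 6- and 12-month intervals that Section 3.10.3.1 already defines and Section 3.2.4 says will be calculated.
2. State the denominator for these rates: subjects who entered the interval but discontinued before its end stay in and count as not seizure-free. This must be explicit. The general 6-month rule in Section 3.2.4 includes only subjects whose Evaluation Period reaches the last day of the interval. For seizure freedom that section refers to Section 3.10.3.1, whose by-interval definition gives no denominator of its own.
3. For the overall Evaluation Period figure, choose one of two courses. Either let Criterion 1 be met only by completion (FV), or relabel the row as no seizures while on study, split it by FV and EDV, and show follow-up time beside it.

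The cost is SAP wording, one derivation flag and a few more tables. The reported seizure-free rate would be somewhat lower. Under the FV-only course, a child who leaves after a long seizure-free stay counts as 0 in the overall row; the interval tables still credit the intervals that child completed.
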